12.2 Sampling time points and additional tests

With the sponsor's approval, additional time points may be introduced, and changes to time points may be made, if we have reason to believe that the change might improve the quality of the data (for example, if we believe that an important effect of the IMP is occurring at a time when no measurements are scheduled), or if extra procedures are needed in the interest of subject safety. However, the total volume of blood taken in the trial will not exceed the value given in section 12.5. Any additional urine collections may include continuous, total collections, if necessary. An additional 48 hours' residence in the ward, and additional outpatient visits, will be permitted, in the event of a technical failure, and/or if extra observations or samples of blood or urine are needed.

Extra procedures and changes to time points which have a significant impact on the scientific value and/or safety of the trial participants will be implemented only after approval of a substantial amendment from the Regulatory Authority (MHRA), unless the changes constitute an urgent safety measure.

The following will **not** be regarded as protocol deviations.

Table 5 Acceptable deviation times (Part A)

Procedure	Timepoint	Acceptable deviation
PK blood sampling	Predose on Day 1	Up to 30 min before dosing
	1 h to 3 h post dose	± 10 min of the scheduled time
All other procedures*	Pre-dose on Day 1	Up to 90 min before dosing*
	Up to and including 4 h post dose	± 10 min of the scheduled time
	After 4 h to 24 h post dose	± 15 min of the scheduled time
	Outpatient visits	± 1 day

* samples for urinalysis may be collected anytime from when the subject awakes until the scheduled time.

Table 6 Acceptable deviation times (Part B)

Procedure	Study day	Timepoint	Acceptable deviation
PK blood sampling	Days 1 and 7	Predose	Up to 30 min before dosing
		1 h to 3 h post dose	± 15 min of the scheduled time
All other procedures*	Days 1 and 7	Pre-dose	Up to 90 min before dosing*
		Up to and including 4 h post dose	± 10 min of the scheduled time
		After 4 h to 24 h post dose	± 15 min of the scheduled time
		Days 2–6	Predose
	Day 8	> 24 h post dose	± 1 h of the scheduled time
	Day 9 onward	Outpatient visits	± 1 day

* samples for urinalysis may be collected anytime from when the subject awakes until the scheduled time.

12.3 Follow-up

Subjects will return to the ward about 7 (Part A) or 14 (Part B) days after their (final) dose of trial medication for a follow-up visit. Withdrawn subjects who consent to a follow-up visit will undergo the same procedures (see section 9.4).

The follow-up period may be extended if:

1. a subject has an unresolved AE at the follow-up visit, which, in the opinion of the investigator, merits further follow-up; or
2. new information becomes available that supports an extended follow-up period.

The investigator will decide on the nature of the follow-up. For example, subjects may have a telephone follow-up at which they are asked about AEs, or subjects may be asked to attend extra outpatient visits for additional monitoring of effects of IMP, and for extra safety tests. The extra safety tests might include tests that are not described in this protocol. The investigator reserves the right, during or after the study, to repeat safety tests or to do any extra safety tests that are in the best interest of the subjects. Those extra tests may or may not be described in this protocol.

12.4 Methods

Blood collection

Blood will be taken by venepuncture or via a cannula. Cannulae will be inserted under local anaesthesia with lidocaine 0.5%, for withdrawal of venous blood.

After each blood sample, the cannula will be flushed with 3–5 mL normal saline, to keep it patent. In order to minimise dilution of each subsequent blood sample with normal saline, the following procedure will be used: about 1 mL will be drawn via the cannula into the sampling syringe and discarded. The definitive blood sample will then be taken.

Blood volumes of specific types of samples may vary from those described below, but any change to the sample volumes will not cause the total volume of blood taken during the study to exceed that given in section 12.5.

Samples for laboratory safety tests

Blood will be taken for:

- haematology (2 mL in EDTA)
- biochemistry (3.5 mL in tubes with a gelatin plug)
- serology (3.5 mL in tubes with a gelatin plug)
- serum pregnancy/FSH (3.5 mL in tubes with a gelatin plug; serology sample used at screening)

Blood samples will be collected into 13 × 75 mm tubes. Urine will be collected in Universal containers. Samples will then be transferred to the laboratory. For

logistical reasons, blood and/or urine samples may be collected in tubes other than those stated below.

Processing and analysis of samples for laboratory safety tests

Processing of samples will be done by the HMR Analytical Laboratory in accordance with the laboratory's SOPs.

The HMR Analytical Laboratory will do safety tests on blood and urine samples using instruments interfaced to a validated laboratory information management system (LIMS). Data from analysers that are not interfaced will be entered manually into the LIMS.

Table 7 Laboratory safety tests

Haematology:	Biochemistry:

 • haemoglobin (Hb) • red blood cells (RBC) • mean corpuscular volume (MCV) • mean corpuscular haemoglobin (MCH) • mean corpuscular haemoglobin concentration (MCHC) • haematocrit • white blood cells (WBC) and differential (neutrophils, lymphocytes, monocytes, eosinophils, basophils) • platelets 	
 • urea • creatinine • uric acid • total bilirubin • total protein • albumin • globulin • alkaline phosphatase (AP) • aspartate aminotransferase (AST) • alanine aminotransferase (ALT) • gamma-glutamyl transpeptidase (GGT) • glucose* • phosphate • cholesterol • triglycerides • potassium • sodium • calcium • chloride • C-reactive protein (CRP)
Urinalysis:	

 • dipstick: protein, blood, ketones, glucose, bilirubin, urobilinogen, leukocyte esterase, specific gravity, nitrites, pH • microscopy: only if dipstick test for protein, blood, leukocyte esterase or nitrites is abnormal 	
Serology:	

 • hepatitis B (hepatitis B surface antigen) • hepatitis C antibody • hepatitis C RNA[#] • HIV screen (HIV 1 and 2) 	
* fasting at screening, on Day -1 and at Follow-up
 
[#] performed if result for hepatitis C antibody is positive

Pregnancy tests

Serum pregnancy tests will be done using an immunoenzymatic method.

FSH tests

Serum FSH tests will be done using a chemiluminescent immunoassay method.

Drugs of abuse, alcohol and cotinine tests

Urine will be tested for drugs of abuse, alcohol and cotinine according to the laboratory's SOP. Tests will include: amphetamines, cocaine, opiates, cannabis, barbiturates, benzodiazepines, alcohol and cotinine.

Processing of blood samples for analysis of plasma concentration of Neumifil

5 mL blood will be collected in will be taken into K₂EDTA tubes, and immediately placed on ice. Samples will be centrifuged at 2000 G for 10 min at 4 °C and divided into 2 aliquots of approximately equal volume (minimum of 200 µL in the primary aliquot) in 1.8 mL screw-capped polypropylene cryotubes. Plasma samples will be frozen at about –70 °C or below within 1 h after collection, and stored until dispatch to Alderley Analytical Ltd for analysis.

Processing of blood samples for anti-drug antibody analysis

5 mL blood will be collected in BD Vacutainer® rapid serum 5 mL tubes, and left at room temperature for 5 mins to clot. Samples will be centrifuged at 2000 G for 10 min at 4 °C and stored on ice until they are divided into aliquots. Each sample will be divided into 2 aliquots of approximately equal volume (minimum of 1.5 mL in the primary aliquot) in 2 mL screw-capped polypropylene cryotubes. Serum samples will be frozen at about –70 °C or below within 30 min after collection and stored until dispatch to Kymos for analysis.

Physical examination

Physical examination will be done by a physician. Brief physical examinations will be done at the timepoints in the schedule of procedures (section 12.1) if clinically indicated. The following systems/sites will be examined during brief physical examinations: cardiovascular, respiratory, abdomen, nose examination (including rhinoscopy), and other. Full physical examinations will be given at all other timepoints. The following will be examined during full physical examinations: general appearance; head, ears, eyes, nose and throat; thyroid; lymph nodes; back and neck; heart; chest (including auscultation for crepitations and reduced air entry, and percussion for dullness); lungs; abdomen; skin; and extremities; and the following systems will be assessed: musculoskeletal and neurological.

If the chest examination result is of clinical concern, the subject may be referred to a clinic for investigative chest x-ray (Part B only).

Height and weight

Height and weight will be measured by trained staff at HMR.

Vital signs

Blood pressure and heart rate will be measured using SpaceLabs oscillometric equipment. Measurements will be made with subjects in a supine position; subjects will remain supine for at least 5 min before vital signs are measured.

Tympanic temperature will be measured using digital thermometers.

Respiratory rate will be measured by observation of the chest.

Peripheral arterial oxygen saturation (SpO₂%) will be assessed using pulse oximetry.

Repeat vital signs measurements

During the trial, if vital signs fall outside the ranges below, a physician will review and decide on an appropriate course of action. The procedure will only be repeated if instructed by a physician.

Supine systolic blood pressure:	90–140 mm Hg
Supine diastolic blood pressure:	40–90 mm Hg
Supine heart rate:	40–100 beats/min
Temperature:	35.5–37.8 °C
Respiration rate:	10–16 breaths/min

If the result of the repeat measurement is still out of range, the investigator will decide on an appropriate course of action.

Standard 12-lead ECGs

12-lead ECGs will be recorded using Mortara ELI250c and ELI280 cardiographs. Each recording will be printed on a single A4 page at paper speed 25 mm/sec and calibrated to 10 mm/mV. Recordings will be made with subjects in a supine position; subjects will remain supine for at least 10 min before the ECG is recorded. PR, RR, QRS and QT intervals will be captured on source documents. QT interval will be corrected using Fridericia's formula (QTcF).

During the trial, if ECG values fall outside the ranges below, a physician will review and decide on an appropriate course of action. The procedure will only be repeated if instructed by a physician.

Ventricular rate:	35–100 beats/min	PR interval:	110–220 msec
QRS:	≤ 120 msec	QTcF (men):	≤ 450 msec
		QTcF (women):	≤ 470 msec

If the result of the repeat measurement is still out of range, the investigator will decide on an appropriate course of action.

Forced expiratory volume test

FEV₁ and FVC will be measured using a CareFusion Micro lab MK8 spirometer.

Nasal examination

At screening, subjects will be asked whether any part of the nose is tender, sore, or irritating, and whether their sense of smell is normal for them. An external

examination of the nose will be done, and significant abnormalities or erythema will be recorded. A nasal speculum will be used to inspect the nose and assess whether nasal polyps, inflammation or erythema are present.

At specified times during the study, subjects will be asked whether any part of the nose is tender, sore, or irritating, and whether their sense of smell has changed since the start of the study. An external examination of the nose will be done, and abnormalities, inflammation or erythema will be recorded, as well as any changes from baseline (screening), or the previous examination. A nasal speculum will be used to inspect the nose and assess whether abnormalities, inflammation, or erythema are present, as well as any changes from baseline (screening) or the previous examination.

Subject self-reported dosing experience

Subjects will complete a self-reported dosing and post-dosing questionnaire. Subjects are asked to assess whether they experienced any of the following using a numerical rating scale from 0 to 10:

- Pain or stinging in the nose
- Burning sensation or sensation of heat/hotness in the nose
- Bleeding from the nose
- Sensation of needing to blow their nose
- General irritation in the nose
- Sneezing
- Marked change in the sense of taste or smell
- Unpleasant taste

To reduce variability, subjects will be able to see their previous responses. A copy of the questionnaire can be found in Appendix 1 (section 22).

Nasal wick sampling

Nasal wicks will be used to collect samples of nasal secretions for measurement of cytokines and chemokines (including but not limited to IL-1, IL-3, IL-10, TNF- α , MCP-1 and IP-10), using a multiplex assay.

12.5 Total volume of blood removed

The total volume of blood taken from each volunteer in the trial will be about 52 mL in Part A, and 93.5 mL in Part B, as stated in Table 8 (Part A) and Table 9 (Part B), respectively. Additional blood samples for assay of Neumifil plasma concentration, ADAs, or for laboratory safety tests may be taken as described in section 12.2. No more than an extra 80 mL of blood will be taken from any subject.

Table 8 Planned blood volume (Part A)

Test	Planned number of tests	Volume (mL)	Total planned blood volume (mL)
Haematology	6	2	12
Biochemistry	6	3.5	21
Serology (and FSH)	1	3.5	3.5
Pregnancy*	2	3.5	3.5
Plasma Neumifil	4	2	8
Discard (when using a cannula)	4	1	4
		Total	52 mL

*included in serology sample at screening

Table 9 Planned blood volume (Part B)

Test	Planned number of tests	Volume (mL)	Total planned blood volume (mL)
Haematology	6	2	12
Biochemistry	6	3.5	21
Serology (and FSH)	1	3.5	3.5
Pregnancy*	2	3.5	7
Plasma Neumifil	8	5	40
ADAs	2	5	10
Discard (when using a cannula)	8	1	8
		Total	93.5 mL

*included in serology sample at screening

13 Trial materials

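### The planned blood volumes in section 12.5 do not agree with the protocol's own rows, schedule and methods, and the limit built on them is unclear

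*Combined protocol and SAP*

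**What the plan says.** Section 12.5 puts the blood taken from each volunteer at "about 52 mL in Part A, and 93.5 mL in Part B", and refers to Table 8 (Part A) and Table 9 (Part B). It then permits additional samples as set out in section 12.2, up to 80 mL more per subject.

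Three rows are the same in both tables: "Haematology 6 2 12", "Biochemistry 6 3.5 21" and "Serology (and FSH) 1 3.5 3.5". The pregnancy row differs. Table 8 has "Pregnancy* 2 3.5 3.5" and Table 9 has "Pregnancy* 2 3.5 7", both with a footnote saying that the screening test uses the serology sample. Table 8 has four PK samples at 2 mL; Table 9 has eight at 5 mL. Each table has a discard row that applies when a cannula is used.

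On PK samples, section 12.4 says "5 mL blood will be collected in will be taken into" EDTA tubes and makes no distinction between Parts A and B.

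Section 12.2 says that "the total volume of blood taken in the trial will not exceed the value given in section 12.5". Section 12.4 applies the same limit to changes in sample volume.

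**The concern.** A planned blood volume is a simple sum, and here it also serves as a control: two other sections refer to it to limit added samples or larger tubes. If the base figure is too low, staff cannot tell how much sampling is still allowed, and the ethics committee and regulator, who review the trial proposal, see a planned volume below what the procedures require.

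There are three separate faults. Table 9 does not equal the sum of its own rows. The two tables treat an identical pregnancy line differently. Table 8 and section 12.4 give different PK sample volumes. On top of these, it is unclear what the limit is.

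**Working it through.** **Inputs.** Row counts and volumes are from Tables 8 and 9. The PK tube volume is from section 12.4. Test counts are from the schedules in sections 12.1.1 and 12.1.2. The schedules support the other counts: six laboratory safety samples in each part, four PK samples in Part A (predose, 1, 2 and 3 h), eight in Part B (the same times on Days 1 and 7), and two ADA samples in Part B.

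**Step 1: Part A as printed.** 12 + 21 + 3.5 + 3.5 + 8 + 4 = 52 mL. The stated figure reproduces, and it includes the 4 mL discard row.

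**Step 2: Part B as printed.** 12 + 21 + 3.5 + 7 + 40 + 10 + 8 = 101.5 mL. The stated 93.5 mL does not reproduce. Without the discard row, 101.5 − 8 = 93.5 mL, an exact match. The total therefore leaves out a row that the table prints, which is the opposite of Table 8's treatment. The gap is 8 mL, and 8 / 93.5 = 8.6%.

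**Step 3: the pregnancy row.** Both schedules mark three tests: screening, Day −1 and follow-up. Only the screening test shares the serology tube, so two further tubes are drawn: 2 × 3.5 = 7 mL. Table 9 agrees with this and Table 8 does not. Correcting Table 8 gives 52 + 3.5 = 55.5 mL (3.5 / 52 = 6.7% more), whatever the PK volume.

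**Step 4: the Part A PK volume.** At 5 mL, 4 × 5 = 20 mL replaces 4 × 2 = 8 mL, which adds 12 mL.
- With the pregnancy row as printed: 52 + 12 = 64 mL (12 / 52 = 23% more).
- With the pregnancy row corrected: 55.5 + 12 = 67.5 mL (15.5 / 52 = 30% more).

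**Step 5: totals by type of subject.** Pregnancy tests are for women of child-bearing potential only, and the discard applies only with a cannula. The totals below use 7 mL for the pregnancy row.

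| Pregnancy tests | Cannula | Part A, 2 mL PK | Part A, 5 mL PK | Part B |
|---|---|---|---|---|
| No | No | 44.5 | 56.5 | 86.5 |
| No | Yes | 48.5 | 60.5 | 94.5 |
| Yes | No | 51.5 | 63.5 | 93.5 |
| Yes | Yes | 55.5 | 67.5 | 101.5 |

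**Step 6: the two readings of the limit.**
- Limit excludes the 80 mL (52 and 93.5 mL). Part B subjects bled by cannula exceed it (94.5 or 101.5 mL); those bled without one do not. In Part A, all four types exceed it at 5 mL per PK sample, but only cannulated women of child-bearing potential exceed it at 2 mL.
- Limit includes the 80 mL: 52 + 80 = 132 mL and 93.5 + 80 = 173.5 mL. The highest planned totals, 67.5 and 101.5 mL, do not reach it.

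**The case against.** The strongest objection concerns the limit. A reader might infer that a subject bled exactly to plan breaks a ceiling set by the protocol. The documents do not establish that. Section 12.5 itself permits additional samples and points to section 12.2 for them. If the ceiling were 52 or 93.5 mL alone, no such sample could be taken, so including the 80 mL is the reading that makes the sections consistent. The limits in sections 12.2 and 12.4 are also written for added time points and changed volumes, and the 52 mL is stated as approximate. This stands, and what remains is an ambiguity. Even on the wider reading the base is wrong: the excess over the stated totals would use up to 8 mL of the 80 mL in Part B, and up to 3.5 or 15.5 mL in Part A, depending on the PK volume.

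A reader might also take 64 to 67.5 mL as the true Part A total. That holds only if the 5 mL in section 12.4 governs. Section 12.4 lets sample volumes vary and asks for only 200 µL in the primary plasma aliquot, so 2 mL is not implausible. With 2 mL the range is 52 to 55.5 mL.

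Nor can one conclude that subjects were told too low a figure. The subject information is not among the documents.

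Finally, the amounts are small. The blood-loss exclusion criterion is set at 400 mL in 3 months, and no endpoint or analysis depends on these totals. That bears on how serious the point is, but not on whether the totals are right.

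**Conclusion.** The stated volumes are wrong or unsupported as written.

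- **Part B:** the Table 9 total should be 101.5 mL, not 93.5 mL. This needs no assumption beyond adding the printed rows. The stated 93.5 mL is the maximum only for subjects bled without a cannula.
- **Part A:** the pregnancy row is too low by 3.5 mL, which rests on the three tests marked in the schedule. The total is then 55.5 mL if 2 mL per PK sample is intended and 67.5 mL if 5 mL is. The documents do not say which volume applies.
- **Limit:** it is not defined clearly enough to tell whether planned sampling can exceed it.

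This is more than clerical, because other sections rely on the figures as a limit. It is a defect of accuracy and compliance; the documents show no hazard to subjects. It should be corrected.

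**What to change.** 1. Correct the Table 9 total, and the Part B figure in the text of section 12.5, to 101.5 mL.
2. Correct the pregnancy row in Table 8 to 7 mL.
3. Reconcile the Part A PK sample volume between Table 8 and section 12.4, then restate the Part A total in Table 8 and the text: 55.5 mL at 2 mL per sample, 67.5 mL at 5 mL.
4. State in section 12.5 whether the limit cited in sections 12.2 and 12.4 includes the extra 80 mL.
5. Check that any volume quoted to subjects matches the corrected totals.

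The cost is edits to two tables and a sentence or two, with no new procedure. The only downside is that the stated volumes become slightly less favourable.

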13.1 Identity of test product

[REDACTED]

[REDACTED]

[REDACTED]

The sponsor will provide to HMR a certificate of analysis for the test product, and, if applicable, any other documents and data required by HMR's Qualified Person (QP) to release batches of IMP.

13.2 Packaging and labelling

The trial medication will be prepared, packaged, and labelled by the HMR Pharmacy, in accordance with The Rules Governing Medicinal Products in the European Union, Volume 4: Good Manufacturing Practice (GMP), and with HMR's Manufacturing Authorisation for IMPs (MIA[IMP]). The IMP labels will include all the information required by Annex 13 to GMP¹¹.

13.3 Storage and accountability of IMP

The IMP will be stored and accounted for according to GMP and HMR SOPs.

At the end of the trial, all unused IMP supplies will be returned to the sponsor or destroyed in accordance with the sponsor's instructions. Further details will be provided in the IMP handling manual.

14 Adverse events

14.1 Definitions of adverse events

Adverse event (AE)

Any untoward medical occurrence in a patient or clinical trial subject administered a medicinal product and which does not necessarily have a causal relationship with that treatment.

Adverse drug reaction (AR)

All untoward and unintended responses to an IMP related to any dose administered. Note that, according to the ICH Guideline for Good Clinical Practice (ICH GCP), a causal relationship between the medicinal product and the AE is at least a reasonable possibility, ie a relationship cannot be ruled out.

Unexpected adverse drug reaction

An AR, the nature or severity of which is not consistent with the applicable product information (eg Investigator's Brochure [IB] for an unauthorised investigational product, or summary of product characteristics for an authorised product).

Serious adverse event (SAE) or serious adverse drug reaction (SAR)

An AE or AR that:

- is fatal;
- is life-threatening;

- requires or prolongs inpatient treatment;
- results in persistent or significant disability or incapacity; or
- is a congenital anomaly or birth defect.

Note:

the term ‘life-threatening’ in the definition of ‘serious’ refers to an event or reaction in which the patient was at risk of death at the time of the event; it does not refer to an event or reaction which hypothetically might have caused death had it been more severe; and

in accordance with the ICH Guideline on Clinical Safety Data Management: Definitions and Standards of Expedited Reporting, events or reactions that are not immediately life-threatening or may not result in death or hospitalisation but might jeopardise the subject or require intervention to prevent one of the other outcomes listed above, should usually be considered serious.

Significant AE or AR

An AE or AR which is not serious but is otherwise significant. The following should normally be considered significant:

- a marked haematological or other laboratory abnormality;
- an AE or AR that leads to an intervention, including withdrawal of drug treatment, dose reduction or significant additional concomitant therapy; or
- any AE or AR that the investigator considers to be significant.

